4.3.4 Study Day

For purposes of calculating study day, the day of randomization is defined as Day 0. Study Day will be calculated as [date of event – date of randomization + 1].

4.3.5 Visit Windows

Nominal study visits (days or weeks relative to Baseline) as collected per the protocol schedule of events will be used to summarize data. Ranges for study day intervals (“windows”) will not be used to re-assign visit numbers in relation to the start of therapy. If there is more than one valid measurement for a selected visit after the baseline visit, the average of the values collected will be used. However, for any safety analyses intended to identify outliers (including, but not limited to, shift tables), the most extreme value instead of the average of the values collected will be used; and values from all visits (including unscheduled measurements) will be included in these analyses.

4.3.6 Multiplicity

There is a single primary efficacy endpoint (a composite of CV death, nonfatal MI, nonfatal stroke, coronary revascularization, or hospitalization for unstable angina) and one primary comparison (Placebo vs. 4 g /day AMR101) defined in the primary objective. Formal

statistical testing for key and other secondary endpoints will be performed for the final analysis, either at the planned completion at 1612 primary events or in case of an early stop for efficacy at one of the two interim analyses, and will be carried out in a hierarchical fashion if and only if the primary endpoint meets statistical significance. The hierarchy of secondary endpoints is given in Section 3.2.1.2.

The planned interim analyses are based on a group sequential design with O'Brien-Fleming boundaries generated using the Lan-DeMets alpha-spending function at approximately 60% and 80% of the targeted 1612 events. The use of the spending-function allows for possible deviations from the planned event number at the time of the interim. If the interim analyses are carried out exactly at the planned 60% and 80% milestones, then the resulting one-sided alpha-levels at each of the two interim analyses and the final analysis are:

- 0.0038 at the 60% milestone (967 events),
- 0.0110 at the 80% milestone (1290 events), and
- 0.0211 at the 100% milestone (1612 events).

A complete description of the group sequential design details is described in the iSAP ([Appendix A](#)).

The alpha level for the final analysis either at the planned completion at 1612 primary events or in case of an early stop for efficacy will be obtained from the O'Brien-Fleming boundaries generated using the Lan-DeMets alpha-spending function. If the primary efficacy endpoint test described in Section 4.7.1.1 meets statistical significance at this alpha-level, then the testing will be carried out hierarchically for the key secondary and the other secondary endpoints at the same alpha level used for the primary endpoint. All analysis beyond the primary or the last endpoint meeting statistical significance at this alpha-level will be considered as exploratory. Further details on the alpha-level to be used for the final analysis are given in Section 4.5.

Since the results from the analysis of the tertiary endpoints are intended to be supportive rather than pivotal evidence of drug efficacy and safety, all tertiary efficacy endpoint analysis will be considered exploratory and statistical testing will be carried out at the nominal 5% level without adjustment.

4.4 Interim Analyses

Two interim analyses are planned for the primary efficacy endpoint using adjudicated events when adjudication of approximately 60% (967 events) and approximately 80% (1290 events) of the total number of primary endpoint events planned (1612) is reached. The planned interim analyses are based on a group-sequential design and are described in the iSAP ([Appendix A](#)).

The interim results of the study will be monitored by an independent DMC. The analyses will be performed by an independent statistical team that is unblinded to the treatment assignment and will be reported only to the DMC. The unblinded information will not be released to the

Sponsor before the completion of the study unless extraordinary circumstances arise and, under such circumstances, procedures for maintaining confidentiality will be described in a written agreement with the DMC.

If the study is terminated early following an interim analysis, patients will be notified promptly and brought in for their final close-out visit, and the final analyses of efficacy and safety will include all data through their final visit. Further details are given in Section 4.5.

4.5 Final Analysis Following an Interim Analysis Early Stop Decision

If the decision is taken to terminate the study at one of the two planned interim analyses, the study will enter the closeout phase. During this phase, which extends from the DMC interim analysis meeting until the final database lock, additional adjudicated events may arrive. The final analysis, being based on the totality of the evidence, will include these additional events, resulting in an increase in the information fraction (of the pre-specified 1612 events) from what the information was at the time of the interim decision making. The significance level for the formal hypothesis testing at the final analysis will then be recomputed from the Lan-DeMets error spending function at the new information fraction while ignoring the look at which the efficacy boundary was crossed for the DMC decision-making purpose (Whitehead, 1992). A few examples of the recomputed alpha level used for the final analysis are given in the Table below:

Table 1. Examples of Recomputed Alpha Levels for Final Analysis

Early Stop IA Number	Number of Events at IA Decision	Number of Additional Events at Closeout	Final Analysis	
			Total Number of Events	α Level
1	967	33	1000	0.0088
1	967	50	1017	0.0095
2	1290	40	1330	0.0272
2	1290	60	1350	0.0286

IA=interim analysis

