4. STATISTICAL METHODOLOGY

4.1 Determination of Sample Size

The initial sample size estimation (protocol v1.0) was based on the assumption that the primary composite endpoint (time from randomization to the first occurrence of CV death, non-fatal MI, non-fatal stroke, coronary revascularization, or unstable angina requiring hospitalization) would be relatively reduced by approximately 15% with AMR101 from an event rate by 4 years of 20.8% (5.2% per year) in the placebo group (which corresponds to a hazard ratio of 0.85). The updated sample size calculation is based on assumptions of constant hazard, asymmetric recruitment rate over time and without factoring for dropouts. A risk reduction corresponding to a hazard ratio of 0.85 (AMR101 vs. control) is assumed. 1612 events would be required to detect this hazard ratio with approximately 90% power with two-sided alpha-level at 5% and with two interim analyses.

The recruitment period is assumed to be approximately 4.2 years with 20% recruitment in the first year, 40% in the second year, 20% in the third year, 19% in the fourth year and the remaining 1% in the last 0.2 years. The expected maximum study duration is estimated at 6.5 years unless the trial is terminated early for efficacy or safety issues. A one-year event rate of 5.2% (hazard = 0.053) in the control arm is also assumed. Under these assumptions the number of patients to be enrolled is $N = 7990$.

Two interim analyses are planned after approximately 60% (967) and approximately 80% (1290) of the primary events have occurred (see iSAP in Section 6.1 [[Appendix A](#)] for description of the interim analyses).

Since this is an events-driven trial, the ‘sample size’ is the number of events rather than the number of patients. The number of events that occur depends primarily on three factors: how many patients are enrolled, the combined group event rate, and how long the patients are followed. Because of the difficulty in predicting the combined event rate, the sponsor will monitor that event rate as the trial progresses. If the combined event rate is less than anticipated, either increasing the number of patients, extending the length of follow-up, or a balance of adjusting both factors may be necessary to achieve the sample size of 1612 events.

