4.3 Statistical Considerations

4.3.1 General Statistical Considerations

All statistical analyses and data summaries are to be generated according to this SAP. Any deviations from this SAP will be documented in the CSR.

All null hypotheses will be defined as no treatment difference. All statistical tests for the efficacy outcomes will be performed at the two-sided 5% significance level, unless otherwise noted. The iSAP will utilize one-sided testing for efficacy at the 0.025 level for interim analyses, the operating characteristics of which are identical to those of a corresponding group sequential design with a two-sided alpha level of 0.05.

Summary statistics will be presented by treatment group and by visit where appropriate. Data will be presented “as-observed”, unless otherwise specified. Continuous data will be summarized with descriptive statistics: count (n), number of missing values (n-missing), mean, standard deviation (SD), median, minimum, and maximum. Categorical data will be described using frequencies and percentages, including a category for missing values where appropriate. Percentages are based on the number of patients in the analysis set. All meaningful patient data collected in the database will be listed. Listings will be sorted by patient within center/site.

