7 STATISTICAL INFERENCE FOLLOWING AN STOP EARLY AT AN INTERIM ANALYSIS

If the decision is taken to terminate the study at one of the two planned interim analyses, the study will enter the closeout phase. During this phase that extends from the interim analysis meeting of DMC until the final database lock, additional adjudicated events may arrive. The final analysis, being based on the totality of the evidence, will include these additional events, resulting in an increase in the information fraction (of the pre-specified 1612 events) from what the information was at the time of the IA. The significance level for the formal hypothesis testing at the final analysis will then be recomputed from the Lan-DeMets error spending function at the new information fraction. Stage-wise adjusted p-values and confidence intervals consistent with group sequential boundaries computed using the Lan-DeMets spending function (Tsiatis 1984, Kim 1987) will be calculated.

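### SAP Table 1: the two final alpha levels after a stop at interim 2 are cumulative alpha spent (0.0272, 0.0286), not the levels the stated rule gives (0.0249, 0.0263)

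*Combined protocol and SAP*

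**What the plan says.** The design is group sequential, with "boundaries generated using the Lan-DeMets alpha-spending function at approximately 60% and 80% of the targeted 1612 events" (SAP 4.3.6). That section lists one-sided levels of 0.0038 at 967 events, "0.0110 at the 80% milestone (1290 events), and" 0.0211 at 1612 events. It takes the final level from the O'Brien-Fleming boundaries, both for planned completion and for an early stop, and applies that level to the key secondary and the other secondary endpoints in sequence.

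SAP 4.5 covers events that arrive during closeout after a stop. The level is recomputed at the new information fraction "while ignoring the look at which the efficacy boundary was crossed for the DMC decision-making purpose". Its Table 1 gives four examples:

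- stop at interim 1: 0.0088 at 1000 events and 0.0095 at 1017;
- stop at interim 2: 0.0272 at 1330 events and 0.0286 at 1350.

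The alpha column does not say whether it is one- or two-sided.

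iSAP section 7 also has the level "recomputed from the Lan-DeMets error spending function at the new information fraction", but without the clause about ignoring a look. iSAP Table 1 shows cumulative alpha spent and the boundary p-value in separate columns: 0.0122 and 0.0110 at the second look, 0.0250 and 0.0211 at the third.

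**The concern.** Cumulative alpha spent and the nominal test level are the same number only when no earlier look remains in the calculation. After a stop at interim 1, dropping the crossed look leaves none. After a stop at interim 2, the 967-event look was tested and not crossed, and it has used one-sided 0.0038. The nominal level at closeout must then be smaller than the spend, as it is in every later row of the iSAP tables. The interim-2 rows of SAP Table 1 nevertheless match the spend.

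This number would be the pass/fail line for the primary endpoint after such a stop, and for each secondary endpoint reached in the sequence. A p-value between 0.0249 and 0.0272 at 1330 events would be significant by the table and not by the rule. If the text, the table and the iSAP disagree, the choice between them could end up being made after unblinding.

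**Working it through.** **Inputs.** Maximum 1612 events; interims at 967 and 1290 (SAP 4.3.6). One-sided 0.025, equivalent to two-sided 0.05 (SAP 4.3.1). Closeout counts of 1000, 1017, 1330 and 1350 (SAP Table 1).

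**Formulas.** With t = events/1612, the one-sided O'Brien-Fleming-type spend is a(t) = 2[1 − Φ(2.2414/√t)], where 2.2414 is the 0.9875 normal quantile. Each boundary c is solved in turn so that the null probability of crossing at any retained look up to t equals a(t), with corr(Zᵢ, Zⱼ) = √(tᵢ/tⱼ). The critical hazard ratio is exp(−2c/√events).

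**Step 1: reproduce the plan's design.** At fractions 0.60, 0.80 and 1.00:

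- spend 0.0038, 0.0122, 0.0250;
- boundaries 2.669, 2.289, 2.031;
- one-sided levels 0.0038, 0.0110, 0.0211;
- hazard ratios 0.842, 0.880, 0.904.

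These match iSAP Table 1. (Using 1290/1612 exactly gives 0.0111 at the second look, a rounding difference.)

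**Step 2: reproduce SAP Table 1 as two-sided spend, 2a(t).**

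- 1000 events: t = 0.6203, 0.00886 (printed 0.0088, which results if t is rounded to 0.62).
- 1017 events: t = 0.6309, 0.00955 (printed 0.0095).
- 1330 events: t = 0.8251, 2.2414/√0.8251 = 2.4676, a = 0.01360, doubled 0.0272 (as printed).
- 1350 events: t = 0.8375, 2.2414/√0.8375 = 2.4493, a = 0.01431, doubled 0.0286 (as printed).

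For the first two rows spend is also the correct level, because no earlier look remains. They agree to within rounding.

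**Step 3: apply the rule in SAP 4.5 to a stop at interim 2.** Drop the 1290-event look, keep the 967-event look, and solve P(Z₉₆₇ ≥ 2.669 or Z_final ≥ c) = a(t).

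- 1330 events: correlation √(967/1330) = 0.853, c = 2.2435, one-sided 0.01243, two-sided 0.0249.
- 1350 events: correlation √(967/1350) = 0.846, c = 2.2220, one-sided 0.01314, two-sided 0.0263.

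**Step 4: apply iSAP section 7 literally.** Keeping both interim looks gives two-sided 0.0201 at 1330 events and 0.0213 at 1350.

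| Closeout events | SAP Table 1 | Rule in SAP 4.5 | iSAP 7, read literally |
|---|---|---|---|
| 1330 | 0.0272 | 0.0249 | 0.0201 |
| 1350 | 0.0286 | 0.0263 | 0.0213 |

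**Step 5: size.** 0.0272/0.0249 and 0.0286/0.0263 are both about 1.09. The critical hazard ratio moves from 0.884 to 0.886 at 1330 events and from 0.886 to 0.888 at 1350. Testing at the printed level with the 967-event look kept uses a cumulative two-sided 0.0294 where the function allows 0.0272, and 0.0308 where it allows 0.0286.

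**Step 6: error rate of the procedure actually run.** For the primary endpoint, 20 million null trials were simulated per scenario, following the interim boundaries and then the relevant final level. Overall two-sided error with the printed and the corrected levels was 0.0467 and 0.0461 (closeout at 1330), and 0.0461 and 0.0456 (closeout at 1350).

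For one truly null secondary endpoint, the correlation with the primary was varied from 0.3 to 1 and the primary effect from none to beyond the design value. The highest one-sided error was about 0.0234 (printed) and 0.0231 (corrected) with closeouts at 1000/1330 events, and about 0.0230 and 0.0228 with closeouts at 1017/1350.

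**The case against.** A reader might infer that type I error is breached, above all for the secondary endpoints, which have no interim boundary of their own. The documents do not support that. A secondary endpoint is tested once, at the final analysis, and only if the primary and every endpoint ranked above it succeed. The simulated error stays below one-sided 0.025. For the primary, a stop at interim 2 already requires one-sided p below 0.0110, stricter than either candidate closeout level. The 0.0294 in step 5 omits that requirement, so it measures departure from the spending function and is not the trial's error rate. This part of the objection stands in full.

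It can also be said that SAP 4.5 rests on a cited paper on overrunning, that its authors may have meant the spend itself to be the level, and that Table 1 only gives examples. The paper is not available here. As written, however, the text ignores one look, SAP 4.3.6 takes the level from the boundaries, and iSAP Table 1 keeps spend and level apart. At 1612 events the interim-2 method would give one-sided 0.025 where the plan uses 0.0211. Examples also show a programmer how to apply the rule, so these two would pass the error on.

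The missing sidedness label is minor. SAP 4.3.1 says "All statistical tests for the efficacy outcomes will be performed at the two-sided 5% significance level, unless otherwise noted" and adds that "The iSAP will utilize one-sided testing for efficacy at the 0.025 level for interim analyses". SAP 4.7.1.1 also calls the primary's level two-sided. iSAP section 7 further promises stage-wise adjusted p-values and confidence intervals, but these do not settle which threshold applies.

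**Conclusion.** The two interim-2 rows of SAP Table 1 are wrong under the plan's own rule: 0.0272 and 0.0286 should be 0.0249 and 0.0263. The excess is about 9% of the threshold, or about 0.002 on the critical hazard ratio. Together with iSAP section 7, the documents support three thresholds for the same stop, and whichever is used carries over to the ranked secondary endpoints.

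The scope is narrow. Interim-1 stops and completion at 1612 events are unaffected, and too lenient here means against the stated rule and spending function. No breach of the overall 5% error rate is shown.

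The levels assume looks at exactly 967 and 1290 events and the closeout counts in Table 1. The secondary-endpoint result also assumes that secondary events accrue at the same information fractions as primary events, which the documents do not state. This is a should-fix: the numerical effect is small, but a confirmatory threshold ought to have one value before unblinding.

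**What to change.** 1. In SAP Table 1, replace 0.0272 with 0.0249 (1330 events) and 0.0286 with 0.0263 (1350 events), and label the alpha column two-sided.
2. In SAP 4.5, add that earlier looks that were not crossed are kept when the nominal level is solved, and that this level, not the cumulative spend, is the test level.
3. Put the same rule in iSAP section 7.

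If the sponsor did intend to ignore all earlier looks, SAP 4.5 and the iSAP should say so and justify it, since the present wording says otherwise.

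The cost is two cells, one label and a sentence in each document, settled before unblinding. The event target, the interim boundaries and the planned final level do not change. The sponsor gives up only the small leniency in the printed figures.

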4.6 Summary of Study Population Data

4.6.1 Patient Disposition

The number and percentage of patients will be tabulated for each of the following categories for each treatment group:

- Screened (total only);
- Re-screened and reasons for re-screening (total only);
- ITT overall and by stratification factors (CV risk, ezetimibe use, and geographical region);

- mITT population; overall and by stratification factors (CV risk, ezetimibe use, and geographical region);
- PP population; overall and by stratification factors (CV risk, ezetimibe use, and geographical region);
- Safety population;
- Patients who complete the study;
- Patients who terminated from the trial early and the primary reason for early termination.
- Patients who terminated the trial early; prior to having a confirmed primary endpoint event.
- Patients with complete follow-up, defined as those for whom all components of the primary endpoint have been ascertained during the entire observation period (or until death).
- Patients who, at the time of study completion, were discontinued from study drug prematurely, but continued within the study (i.e. ODIS patients), along with the primary reason.

4.6.2 Protocol Deviations

All instances of protocol non-compliance will be tracked during the study and a list of protocol deviations will be reviewed in a blinded manner by the Sponsor prior to database lock. Major deviations resulting in exclusion of the patient from the Per Protocol population will be determined. Protocol deviations will be presented in a data listing and summarized by type using counts and percentages by treatment group.

4.6.3 Demographics and Baseline Characteristics

Demographic and baseline characteristics, including age, gender, ethnicity, race, height, body weight, body mass index (BMI), diabetes, hypertension, metabolic syndrome, overweight/obese/normal according to BMI, and diabetes plus obesity will be summarized using descriptive statistics by treatment group in the ITT population.

Demographic data and baseline characteristics will be also compared between treatment groups for the mITT population and PP population. Differences in demographic and baseline characteristics will be tested using a chi-square for categorical variables and a t-test for continuous measures. The p-values will be considered descriptive, primarily as an assessment of the balance between groups. Age in years will be calculated using the date of randomization (Visit 2) and the date of birth.

4.6.4 Cardiovascular Risk Category

Factors determining the cardiovascular risk category (1 or 2) at randomization will be summarized by treatment group using counts and percentages for the ITT and Modified ITT populations.

4.6.5 Smoking and Alcohol History

Smoking status (Never/Former/Current) and Alcohol use (Never/Former/Current) will be presented by treatment group using counts and percentages for the ITT and mITT populations. In addition, the average number of drinks per day for former and current alcohol users will be summarized with descriptive statistics. The number and percentage of patients with a history of alcoholism, previous treatment for alcoholism, and number of years since treatment was completed will be presented.

4.6.6 Cardiovascular History and Procedures, Family History, and Other Significant Medical History

Counts and percentages of patients with each type of cardiovascular disease history will be presented by treatment group for the ITT and Modified ITT populations.

Counts and percentages of patients with a history of cardiovascular procedures (percutaneous transluminal coronary angioplasty [PTCA]/stent, coronary artery bypass graft [CABG], Implantable Cardioverter/Defibrillator, Permanent Pacemaker, Carotid Revascularization and Aorto-iliac or Peripheral Arterial Intervention) will be presented by treatment group for the ITT population. For PTCA/Stent and CABG, whether the procedure was emergent and whether it was successful will be reported. For Carotid Revascularization and Aorto-iliac or Peripheral Arterial Intervention, whether it was performed with a catheter or surgically will be presented.

The number and percentage of patients with a family history of premature coronary heart disease will be summarized by treatment group for the ITT and mITT populations. For patients with a family history, the number and percentage with a male first degree relative < 55 years, female first degree relative < 65 years, or both male and female will be presented.

Other significant medical history will be listed by patient.

